### **Group Modifications**

Describe necessary changes that will or have been made to the study instruments for different groups. For the "immediate" and "immediate with incentives" groups, the post-trial assessment will include measures about the Implementation and Technical Merit of the app (FIM, AIM, IAM, SUS listed above). These items will not appear on the "waitlist" group survey because those participants will not have used the app. Those who served in the armed forces will be asked to answer additional demographic questions (attached) related to their time in service.

### **Method for Assigning Subjects to Groups**

Describe how subjects will be randomized to groups.

The research team will use block randomization to assign participants into one of three groups. Randomization will occur after a participant submits their Informed Consent through REDCap. Their name will be added to a blocked randomization spreadsheet, and they will be assigned to one of the three treatment groups.

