First responders, soldiers and veterans will be invited to take a brief screener survey on REDCap to determine whether they are eligible to participate in the trial. If they meet our inclusion criteria, they will be prompted with an Informed Consent. The Informed Consent, like the screener, will be administered through REDCap. After giving consent, participants will fill out a baseline survey on REDCap. The baseline assessment will contain between 123 - 135 questions, depending on whether the participant served in the military and was deployed, and will take participants approximately 20-30 minutes to complete. Participant demographics will be collected during this assessment and stored in REDCap. Data will be de-identified for the purposes of later analysis. No identifiers will be stored after the study is completed. Participants will receive \$50 in compensation for completing this survey, remitted through a Greenphire ClinCard®. Consented participants will receive an email additional from the research team asking them to schedule a virtual Intake meeting. They will be furnished with a link to a calendar management software, such as Microsoft Bookings to select a date and time that works best with their schedule. Intake meetings will be held one-on-one over Zoom and conducted by the Clinical Research Coordinator. They will be brief, about 20-30 minutes, and will not be recorded. Participants will be briefed on the GUIDE App and will have the opportunity to ask any questions they have about the trial. The baseline assessment should be completed prior to this intake meeting, but if it is not, participants will be given time to do so. Those in the immediate and immediate with incentives groups will also be walked through account creation and general app training. A standardized training protocol will be used so that the app is introduced to participants in a uniform and accurate manner.

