During GUIDE account creation, participants will be required to provide their phone number and/or email address. This personal data will be secured by Okta, a third-party authentication provider, and stored separately from app data. Screenshots of this process can be found in the GUIDE Account Creation document attached to this application. When the meeting is over, all participants will receive an email from the research team with a link to a calendar management software, such as Microsoft Bookings, requesting that they schedule their post-trial meeting for 4-5 weeks out from the intake meeting. During the trial period of 4 weeks, participants in the immediate and immediate with incentives groups will have full access to the GUIDE App. To get started, the app will prompt participants to answer a series of onboarding questions about themselves, including their goals, wellness experience and demographic information (see attached GUIDE Onboarding Process). Based on their responses, participants will be assigned Courses and Daily Practices; as well as a personalized small group chat, where they can post and comment with likeminded others, anonymously, with the option to share app progress. Courses are composed of lessons, and include topics like Forgiveness, Gratitude, and Self-Awareness. The lessons contain a mix of media including videos, assessments, readings and exercises. Courses and lessons take varying amounts of time to complete, which the participant can see before adding it to their profile. The app also includes three types of Daily Practices including Meditation Practice (a simple timer to help keep participants focused while they meditate), Journal Practice (where participants can catalog their thoughts and reactions to lessons), and a Mood Tracker that participants can view over time (How are you feeling? 1 = Very Sad to 5 = Very Happy). On the home page, participants are invited to track their Wellness Score, based on the Personal Wellbeing Score (PWS), over time to see trends. Screenshots of GUIDE app content, and information about how it works, can be found in the GUIDE App Content document attached. The GUIDE App invites participants to complete assessments that screen for PTSD (PC-PTSD-5), insomnia (ICD-10), anxiety (GAD-7), and alcoholism (AUDIT) in their Courses. Before the assessment is administered, participants must watch a 2-minute video about the selected measure and its effectiveness, why it is used and by whom, and how it is a screener (i.e., not a diagnostic tool) that should be used to determine whether further testing or treatment should be solicited. Scores from these measures are not tabulated or collected by GUIDE. When participants finish filling out the assessment, they are brought to a screen that shows them how to score their own responses. For people needing a higher level of care, the following crises numbers are provided in the app: Suicide and Crisis Lifeline, Veteran Crisis Line, Substance Abuse and Mental Health Services Administration, Disaster Distress Hotline, Red Nacional de Prevencion del Suicido, COPLINE, Firefights Union for PTSD & Mental Health, Frontline Helpline, Fire/EMS Helpline, Safe Call Now, and the All Clear Foundation. Participants assigned to the immediate with incentives group will be asked to complete certain weekly tasks in the app order to receive an Amazon gift card for their participation. Required tasks include visiting the GUIDE App at least four times, completing at least one lesson, posting at least one time, commenting at least one time, and completing at least one wellness check-in. When the four-week trial period is over, participants will receive an email from REDCap with a link to their post-trial assessment survey. The survey for participants in the waitlist will contain 100 questions and take about 20 minutes to complete. The survey for participants in the immediate and immediate with incentives groups will contain 123 questions, including questions about app implementation and technical merit, and will take approximately 20-30 minutes to complete. Participants who have not yet scheduled their post-trial meeting will receive an additional email reminder from the research team, along with a link to a calendar management software, such as Microsoft Bookings. During the post-trial Zoom meeting, participants who have not yet completed their post-trial assessment will be given time to do so. They will get the opportunity to give feedback about the GUIDE App and the trial. The meeting will be brief, about 15 minutes, and will not be recorded. Participants will receive \$50 in compensation for completing this survey, remitted through a Greenphire ClinCard®. The research team will also review a brief Adverse Event Checklist with these participants and record their responses. This checklist contains four questions and is attached to this application. Participants in the immediate and immediate with incentives groups will be told they may delete their account associated with GUIDE and remove the app from their phones. Participants in the waitlist group will get the opportunity access to the GUIDE App at this meeting if they are interested.

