**Procedures**

We plan to conduct a three-armed randomized waitlist pilot feasibility trial with up to 150 participants. 50 will receive immediate GUIDE access (immediate group), 50 will receive immediate GUIDE access with incentives (immediate with incentives group), and 50 will be waitlisted with delayed access to GUIDE (waitlist group). Participants will be recruited from GUIDE's network of contacts including customers, advisers, and agency partners. We plan to recruit approximately 75 participants who are first responders/corrections officers, and 75 participants who are veterans/soldiers. Recruitment will be capped to 75 for each group using REDCap. Though we intend to recruit veterans, we will not be recruiting this population directly through the VA. All participants will be screened for eligibility via a brief REDCap eligibility screener (attached), based on our selected inclusion criteria (i.e., must be a first responder/veteran/soldier, must be employed, must own a compatible smartphone, must not be paid by GUIDE/Nlyten, must not have used GUIDE before). If eligible, REDCap will direct them to a copy of the Informed Consent. Participants will have the option to download this document for their personal files and can contact the research team if they have any questions. After participants give their consent, REDCap will email them with a link to their baseline assessment survey. This assessment is intended to capture a baseline of their wellness and other related factors, as well as their demographic information. The following measures will be included (all attached): demographic questionnaire, the PERMA-Profiler (overall score and all subscales, including Positive emotion, Engagement, Relationships, Meaning, Accomplishment), the Patient Health Questionnaire (PHQ-8) for depression symptoms, the Generalized Anxiety Disorder-7 (GAD-7), World Health Organization Five Well-Being Index

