(WHO-5), Personal Wellbeing Score (PWS), Difficulties in Emotion Regulation Scale Short Form (DERS-SF), the Utrecht Work Engagement Scale (UWES), and the Maslach Burnout Inventory (MBI). Consented participants will receive an additional email from the research team asking them to schedule a virtual Intake meeting. They will be furnished with a Calendly link to select a date and time that works best with their schedule. Intake meetings will be held one-on-one over Zoom and conducted by the Clinical Research Coordinator. They will be brief, about 20-30 minutes, and will not be recorded. Participants will be briefed on the GUIDE App and will have the opportunity to ask any questions they have about the trial. The baseline assessment should be completed prior to this intake meeting, but if it is not, participants will be given time to do so. Those in the immediate and immediate with incentives groups will also be walked through account training and general app training. A standardized training protocol will be used so that the app is introduced to participants in a uniform and accurate manner. During GUIDE account creation, participants will be required to provide their phone number and/or email address. This personal data will be secured by Okta, a third-party authentication provider, and stored separately from app data. Screenshots of this process can be found in the GUIDE Account Creation document attached to this application. The participant will provide their randomly assigned username to the research team during their Intake meeting. The research team will keep a separate spreadsheet, locked and encrypted on Box, to match participant usernames with Study IDs. The participant will schedule their Post-Trial Meeting during the Intake Meeting through a calendar management software, such as Microsoft Bookings. During the trial period of 4 weeks, participants in the immediate and immediate with incentives groups will have full access to the GUIDE App. To get started, the app will prompt participants to answer a series of onboarding questions about themselves, including their goals, wellness experience and demographic information (see attached GUIDE Onboarding Process). Based on their responses, participants will be assigned Courses and Daily Practices; as well as a personalized small group chat, where they can post and comment with likeminded others, anonymously, with the option to share app progress. Courses are composed of lessons on topics such as Forgiveness, Gratitude, and Self-Awareness. The lessons contain a mix of media including videos, assessments, readings and exercises. Courses and lessons take varying amounts of time to complete, which the participant can see before adding it to their profile. The app includes three types of Daily Practices including Meditation Practice (a simple timer to help keep participants focused while they meditate), Journal Practice (where participants can catalog their thoughts and reactions to lessons), and a Mood Tracker that participants can view over time (How are you feeling? 1 = Very Sad to 5 = Very Happy). On the home page, participants are also invited to track their Wellness Score through a wellness check-in, which uses the Personal Wellbeing Score (PWS) administered repeatedly over time to track trends. Screenshots of GUIDE app content described above, and information about how it works, can be found in the GUIDE App Content document attached. The GUIDE App gives participants the option to complete assessments that screen PTSD (PC-PTSD-5), insomnia (ICD-10), anxiety (GAD-7), and alcoholism (AUDIT) in their Courses. Study participants are not required to complete these assessments for the trial. Before the assessment is administered, participants must watch a 2-minute video about the selected measure and its effectiveness, why it is used and by whom, and how it is a screener (i.e., not a diagnostic tool) that should be used to determine whether further testing or treatment should be solicited. Scores from these measures are not tabulated or collected by GUIDE. When participants finish filling out the assessment, they are brought to a screen that shows them how to score their own responses. For people needing a higher level of care, the following crises numbers are provided in the app: Suicide and Crisis Lifeline, Veteran Crisis Line, Substance Abuse and Mental Health Services Administration, Disaster Distress Hotline, Red Nacional de Prevencion del Suicido, COPLINE, Firefights Union for PTSD & Mental Health, Frontline Helpline, Fire/EMS Helpline, Safe Call Now, and the All Clear Foundation. These resources are available through the SOS button, which is highlighted after an assessment is completed. Small group chats are monitored by GUIDE moderators. GUIDE moderators work part-time and possess the following qualifications: Crisis Intervention Training Instructor & Coordinator, Peer Support/Critical Incident Stress Management Counselor, Certified Life Coach, Somatic Practitioner Certification, Trauma Informed Certification. If/when participants post comments and/or assessment results about suicide, moderators will escalate to the Research Team within 24 hours by email. The email will contain the participant's username (no PHI) and details about the escalation. PI [name], a psychologist, will investigate the escalation within 12 hours of receipt and contact the participant by phone and/or email to ensure they are connected to appropriate resources. App engagement will be captured by GUIDE using small group posts, small group comments, lessons completed, courses completed, wellness check-ins and other usage metrics and will be used for analysis by the research team. Data will be encrypted, password protected, and transferred securely from GUIDE to the research team using Box. Participants assigned to the immediate with incentives group will have the opportunity to earn additional

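### Nothing requires the baseline survey to be submitted before randomisation or before the participant learns the group, so some self-reported baselines can be given with allocation known.

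*Combined protocol and SAP*

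**What the plan says.** Under Method for Assigning Subjects to Groups, consent is the only trigger for allocation: "Randomization will occur after a participant submits their Informed Consent through REDCap". The name then goes onto a blocked spreadsheet and a group is assigned.

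The baseline survey has the same trigger. Under Procedures: "After participants give their consent, REDCap will email them with a link to their baseline assessment survey". So does the intake invitation: "Consented participants will receive an additional email from the research team asking them to schedule a virtual Intake meeting". Administration of Surveys and/or Process describes both steps in the same way.

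On timing, both sections set an expectation with an exception: "The baseline assessment should be completed prior to this intake meeting, but if it is not, participants will be given time to do so".

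Administration of Surveys and/or Process also describes the content of the intake meeting. For everyone: "Participants will be briefed on the GUIDE App and will have the opportunity to ask any questions they have about the trial". For the two app arms only: "Those in the immediate and immediate with incentives groups will also be walked through account creation and general app training". The post-trial meeting is then booked for 4 to 5 weeks after intake.

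Primary outcome variable(s) names the PERMA-Profiler overall wellbeing score, which is self-reported. The Analysis Plan describes pre-post analysis by linear mixed models or repeated-measures ANOVA and lists that score among its key measures.

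**The concern.** Participants in a waitlist trial know whether they have the app. The usual protection for a self-reported baseline is to collect it before the group is known. Here allocation, baseline survey and intake invitation all hang on consent, and none depends on another. The permitted late baseline falls at the intake meeting, which is also the first documented point at which the arms are treated differently.

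Someone who has just learned that they are waitlisted may score their wellbeing lower, and someone about to start the app may score it higher. In a pre-post analysis that shift enters the between-arm contrast. A baseline answered in this way cannot be retaken, and covariate adjustment shrinks the bias without removing it. Both reactions raise the app arms' baseline relative to waitlist, so the likelier result is a diluted app effect, though the direction is not assured. The trial is a pilot with no stated power target, but Secondary outcome variable(s) counts the sensitivity of its measures among the feasibility outcomes, and dilution may bear on that.

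A lesser consequence of randomising on consent is that some randomised people may have no baseline at all.

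**Working it through.** **Sequence.** The relevant steps, side by side:

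| Step | Stated trigger or time | Conditional on a submitted baseline? |
|---|---|---|
| Randomisation | Consent | No |
| Baseline survey | Consent; expected before intake, allowed at intake | – |
| Intake invitation | Consent | No |
| Account set-up and training (app arms) | Intake meeting | Not stated |
| Disclosure of group | Not stated | Not stated |

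Within intake, the text mentions the app briefing, then the late-baseline allowance, then the app-arm training, but gives no rule on order. The survey is put at 20–30 minutes and the meeting at 20–30 minutes, so a late survey could fill the whole slot.

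**Size.** The plan has no figure to reproduce. The arm sizes (50 each, so 100 app against 50 waitlist) come from Design. Everything else is assumed:

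- *f*: share of baselines given with the group known
- *δ*: resulting between-arm shift in those baselines, in SD
- *r*: pre-post correlation

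Formulas, in SD units:

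- Bias, change contrast (repeated-measures ANOVA or unconstrained mixed model) = f × δ
- Bias, baseline-adjusted or baseline-constrained model = r × f × δ
- SE, change = √(2(1−r)) × √(1/100 + 1/50)
- SE, adjusted = √(1−r²) × √(1/100 + 1/50)

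At r = 0.6, with √0.03 = 0.1732, SE change = 0.894 × 0.1732 = 0.155 and SE adjusted = 0.8 × 0.1732 = 0.139.

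| f (of 150) | δ | Bias, change | in SE | Bias, adjusted | in SE |
|---|---|---|---|---|---|
| 5% (about 8) | 0.2 | 0.010 | 0.06 | 0.006 | 0.04 |
| 10% (15) | 0.2 | 0.020 | 0.13 | 0.012 | 0.09 |
| 25% (about 38) | 0.3 | 0.075 | 0.48 | 0.045 | 0.32 |

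Sensitivity of the largest case to r:

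| r | SE change | Bias/SE, change | SE adjusted | Bias/SE, adjusted |
|---|---|---|---|---|
| 0.4 | 0.190 | 0.40 | 0.159 | 0.19 |
| 0.6 | 0.155 | 0.48 | 0.139 | 0.32 |
| 0.8 | 0.110 | 0.68 | 0.104 | 0.58 |

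Share needed for a bias of half an SE at δ = 0.3, r = 0.6:

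- Change: 0.5 × 0.155 / 0.3 = 0.26
- Adjusted: 0.5 × 0.1386 / (0.6 × 0.3) = 0.38

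A simulation of 20,000 trials (100 against 50, no true effect, f = 25%, δ = 0.3 with app-arm baselines raised, r = 0.6) gave mean estimates of −0.075 (SD 0.155) for change and −0.045 (SD 0.139) for baseline-adjusted. This confirms the algebra. It is not evidence about the size in this trial.

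**The case against.** The default order is protective. The survey link is emailed after consent, intake is booked separately for later, completion is expected before intake, and $50 is paid for it. A baseline completed as planned precedes any documented difference between arms, so only exceptions are exposed.

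Disclosure before baseline is nowhere documented either. Entry on a staff spreadsheet is not disclosure. The briefing is for all participants and does not in itself reveal the group, and the one arm-specific step is written after the late-baseline allowance. The standardised training protocol and the consent pages are not in the text available and may set an order. The two smaller scenarios give at most 0.13 SE, half an SE needs 26% or 38% of baselines to be affected, and dropout would enlarge the SE and lower these ratios further. Finally, withholding the group would be enough to prevent the bias, so moving randomisation itself goes further than needed.

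Much of this stands. The documents show that a baseline with the group known is not excluded, not that it will happen, and any bias is probably small. What does not fall is the gap itself: sentence order is not a rule, the exception is explicit, and it falls at the meeting where the arms diverge. The remark on moving randomisation is fair as regards this bias, and the fix below offers a minimum version that does not require it. The full order has the added merit that nobody is randomised without a baseline.

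**Conclusion.** The concern holds. The sections that set the sequence (Method for Assigning Subjects to Groups, Administration of Surveys and/or Process, and Procedures) randomise on consent, allow a late baseline at intake, and do not require the survey to be submitted before allocation or disclosure.

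Confidence is high about the missing order and does not extend to the size of any bias. On assumed inputs the bias runs from negligible, when late baselines are few, to roughly half an SE in a change analysis at r = 0.6, when a quarter of baselines are affected with a 0.3 SD shift. The SEs assume that all 150 are analysed. The point should be fixed because it touches the primary variable in an unblinded trial, cannot be undone once it occurs, and is cheap to close.

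**What to change.** State one order in the three sections: eligibility, consent, baseline survey submitted, randomisation, disclosure of group, then app briefing and training.

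If allocating on the spot during a late-baseline intake meeting is impractical, the minimum is to withhold the group, and hold back app briefing and training, until the survey is submitted. Holding back the general briefing is a precaution, since it goes to every arm.

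In either version, record the date and time of baseline submission, randomisation and disclosure, and report how many baselines came after disclosure.

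The cost is protocol wording and a change in the order of steps, with no new measures and no larger target sample. Under the full order, consented people who never complete the baseline are not randomised and must be replaced to reach 150, and late-baseline meetings need live allocation. In both versions such a meeting runs to about 40–60 minutes (20–30 for the survey plus 20–30 for the meeting) or is rebooked. The minimum version avoids live allocation but still leaves some randomised people without a baseline.

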### **Resources necessary for human research protection**

Describe research staff and justify that the staff are adequate in number and qualifications to conduct the research. Describe how you will ensure that all staff assisting with the research are adequately informed about the protocol and their research related duties. Please allow adequate time for the researchers to conduct and complete the research. Please confirm that there are adequate facilities for the research.

The research team includes the Principal Investigator, [name], a Research Assistant Professor in the Penn Center for Mental Health, University of Pennsylvania and Director of the Digital Mental Health @ Penn Working Group. She will direct all research activities on the proposed project. There will also be a dedicated Clinical Research Coordinator, [name], who has a BA in Psychology and prior research experience. She will be responsible for all organizational tasks of the proposed study, including recruitment and scheduling, as well as many routine administrative tasks and data entry. [name], a Senior Research Assistant, will also assist with administrative tasks. All

research staff completed human subjects training and will undergo training on the study protocol with the PI of the study before contact with any human subject data. The Center for Mental Health, UPenn has adequate facilities for the research. The GUIDE App team will assist the research team with the recruitment of first responders, soldiers and veterans, as advised by our research team. The research team will be responsible for enrollment, app training, intake and post-trial meetings with participants, data collection, analysis, and documentation. The research team will also be responsible for participant compensation to all groups, while the GUIDE team will be responsible for providing additional compensation to the immediate with incentives group.

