### Accrual

This proposal involves the recruitment of 150 participants, including about 75 first responders/ corrections officers and 75 soldiers/veterans. Participation will be capped for each group using REDCap. To recruit these participants, the research team will rely on the GUIDE teams agency connections, existing partnerships, customers, and advisers. We do not anticipate difficulty meeting the recruitment and retention goals for this project because we have the GUIDE apps recruitment support, as well as the participant compensation at pre- and post-trial.

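### No allocation concealment is described: consented names go into a blocked spreadsheet used by the same team that recruits participants and runs arm-specific intake

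*Combined protocol and SAP*

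**What the plan says.** The protocol section Method for Assigning Subjects to Groups gives the whole method. "The research team will use block randomization to assign participants into one of three groups". On timing: "Randomization will occur after a participant submits their Informed Consent through REDCap". On mechanism: "Their name will be added to a blocked randomization spreadsheet, and they will be assigned to one of the three treatment groups".

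The section on resources for human research protection describes a small team: the principal investigator, one clinical research coordinator and a senior research assistant. It says "The research team will be responsible for enrollment, app training, intake and post-trial meetings with participants, data collection, analysis, and documentation". Of the coordinator it says "She will be responsible for all organizational tasks of the proposed study, including recruitment and scheduling". Administration of Surveys and/or Process has the coordinator hold the one-on-one intake meetings, in which only the two immediate-access arms are taken through account set-up and app training.

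REDCap already carries the steps before assignment: "The Informed Consent, like the screener, will be administered through REDCap". It also enforces recruitment limits: "Recruitment will be capped to 75 for each group using REDCap". Those limits apply to the two occupational groups (75 first responders or corrections officers, 75 soldiers or veterans), not to the trial arms.

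**The concern.** Concealment means that nobody who can influence a participant's entry knows the next assignment. The plan describes a mechanism but no concealment, and it places that mechanism in a team whose members recruit participants and learn each arm at intake.

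Two routes to selection are left open. First, consents are submitted online, so more than one consented person may be waiting to be entered, and no rule fixes their order. Second, staff may have had contact with a candidate before assignment: the social media recruitment text invites people to email the research team, and the Procedures section lets them ask the team questions at the consent stage.

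At stake is the comparison of app access with waitlist. The primary outcome variable, the PERMA-Profiler overall wellbeing score, is self-reported. Participants know whether they have the app, and no blinding of staff is described. Concealed random assignment is one of the few protections against bias that this design can still have.

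**Working it through.** **1. What the plan gives.** The only figures are the sample sizes: 3 × 50 = 150 by arm and 75 + 75 = 150 by occupation, and both agree. No block size, stratification or list-holder is stated, so the plan has no figure on predictability to reproduce. The block sizes below are assumptions.

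**2. What the sections say together.**
- The allocation section names the research team and a spreadsheet. It is silent on list generation, block size, masking of later rows, entry order and logging.
- The Procedures section states that a different spreadsheet, linking usernames to study IDs, is locked and encrypted. No equivalent statement is made for the randomization spreadsheet.
- The confidentiality sections restrict electronic files to study personnel. That keeps outsiders out; it does not hide the list from the staff who enrol.

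**3. If the list can be read.** Every upcoming assignment is known (100%). Suppose *k* consented people are waiting at the start of a block of 3. The chance that a given arm is among the next *k* rows is *k*/3:
- *k* = 1: 33%
- *k* = 2: 67%
- *k* = 3: 100%

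With three waiting, whoever sets the order could place any one of them in any chosen arm. With one waiting and entered at once, order gives no leverage.

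**4. If later rows are hidden but the block size is fixed and known.** An observer who has seen past assignments guesses the arm with most places left in the block. The chance of being right at each position is (most places left for any arm) / (all places left), averaged over the possible histories.
- Block of 3: (1/3 + 1/2 + 1) / 3 = 0.611
- Block of 6: (1/3 + 2/5 + 1/2 + 8/15 + 3/5 + 1) / 6 = 3.367 / 6 = 0.561
- Block of 9: 0.532, by the same enumeration
- Chance: 1/3 = 0.333

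**5. Assignments known with certainty in the same setting.** With *m* places per arm, these are the places left once only one arm remains in the block. Their expected number is 3*m*/(2*m* + 1) out of 3*m*, a share of 1/(2*m* + 1).

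| Assumed block | Share certain | Of 150 | Best-guess accuracy |
|---|---|---|---|
| 3 | 1/3 = 33.3% | 50 | 61% |
| 6 | 1/5 = 20.0% | 30 | 56% |
| 9 | 1/7 = 14.3% | about 21 | 53% |

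**6. Are past assignments known?** The coordinator holds the arm-specific intake meetings, so she learns each arm after assignment. Knowledge of the block size is an assumption.

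**The case against.** The strongest reply is that this is a gap in a short answer on an ethics form, for a self-described pilot feasibility trial, and not evidence of an open list. Much of that stands. A reader might infer that upcoming arms are visible to staff, that the coordinator holds the list, or that staff choose the entry order. The documents say none of these things. They do not assign randomization to the coordinator, and Data Management gives data entry and database management to research specialists. Tying randomization to consent is compatible with entering people one at a time as they consent.

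The route to selection is also narrower than in a clinic. Eligibility and consent run through REDCap before assignment, so staff are not described as deciding eligibility with the next arm in mind. The first one-on-one contact described is the intake meeting, whose content already differs by arm. The documents therefore give no basis for supposing that staff would place volunteers according to observed distress.

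Nor can one conclude that steering would be undetectable. If consent times are recorded, consent order can be compared with spreadsheet order afterwards. That is a partial check, and the plan does not call for it.

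Finally, the guessing rates measure predictability, not bias. A correct guess matters only if someone can act on it, and no effect on baseline balance or outcome has been estimated.

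What the reply does not answer is that nothing in the plan conceals the list from the enrolling team, fixes the entry order or logs assignments.

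**Conclusion.** The point holds as a weakness of the described method. The plan states a positive procedure, a blocked spreadsheet used by the team that recruits, enrols and runs arm-specific intake, and describes no concealment, entry-order rule or assignment log. Foreknowledge and steering are risks left open, not documented events.

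Their size depends on facts the plan does not give. Foreknowledge is complete if the list can be read. If later rows are hidden, best-guess accuracy is 61%, 56% or 53% against 33% by chance, for blocks of 3, 6 or 9 that are assumed to be fixed and known to the guesser. REDCap screening and consent before assignment lower the risk without removing it. Because the outcomes are self-reported and no blinding is described, the step is worth tightening. If concealment already exists in practice, stating it in the allocation section would settle that part of the point.

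**What to change.** Replace the spreadsheet step in Method for Assigning Subjects to Groups with a concealed release:
- State who generates and who holds the list.
- Use varying block sizes that are not disclosed to enrolling staff, and hide later rows from them.
- Assign strictly in order of consent timestamp, one participant at a time.
- Log each assignment with its time, and make it non-editable.

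Use REDCap's randomization function if it is available. The documents show REDCap running screening, consent and the occupational caps, but not that this function is enabled. Otherwise, have a locked list held by an existing staff member with no participant contact. The documents do not identify such a person, so the protocol would need to name the role.

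The cost is a small amount of set-up work and a short protocol change. The sample size and participant burden stay the same. The documents do not show whether enrolment has begun. If it has, apply the change to the remaining participants and document how earlier ones were assigned, including a comparison of consent order with spreadsheet order where times were recorded.
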